This proposed intervention will not directly deprescribe medications; we will not be randomizing patients to medication discontinuation. Instead, we are testing an intervention to prompt consideration of a clinical decision, analogous to a clinical reminder in the electronic health record prompting the provider to consider appropriate care. We propose an innovative approach to promote medication use review that starts by contacting the patient, not the clinician, yet the ultimate decision remains with the patient-provider dyad.

Study Aim

The study primary aim is to examine the impact of a patient-centered intervention to change provider prescribing (the primary outcome), as determined by the frequency with which medications are either deprescribed or de-escalated. Our primary outcome will be the composite of deprescribing and de-escalation of target medications, identified in pharmacy dispensing records of the Corporate Data Warehouse (CDW).

Hypothesis

The hypothesis is deprescribing will be greater for Veterans receiving the intervention brochure than for those in the historical control group.

Study sites

We will target Veterans at three primary care sites who meet eligibility criteria and are prescribed the target medication at the time of their scheduled primary care visit (in-person, video technology-based, or telephone clinics). These sites were selected based upon ability to recruit adequate samples, geographic variability, and patient population. We will include all PCPs at VA Medical Centers (VAMCs) and Community Based Outpatient Clinics (CBOCs), except for resident clinicians, as these trainees are likely to turn over during the intervention.

Randomization

Previous research, including our pilot study, revealed differences in deprescribing tendencies across providers. Thus, although our intervention intends to engage patients, our study design prioritizes comparisons of patients within the same provider to maximize power. At each intervention site, individual PCPs will be randomized to the sequence of medication cohorts. We will randomize PCPs to one of the three medication groups at the beginning of the first (month 1) and second (month 7) window and assigned them to their

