remaining medication group at the start of the third (month 13) window. Our primary comparisons are between “brochure-intervention” patients and “baseline” patients (matched in terms of eligibility) from the same provider. Each patient will only have one opportunity to receive a brochure, even if they subsequently meet eligibility criteria for receipt of a second, different brochure. This allows equal exposure to the intervention for all Veterans since the impact of a second brochure might be influenced by the first brochure.

Although our primary comparison is between patients of the same provider pre- and post-intervention, we will also collect data at non-equivalent control sites matched by geography who will not receive the intervention; all data on control patients will be from the Corporate Data Warehouse (CDW). Including additional control sites will allow us to address potential temporal trends in deprescribing over the timeframe of our study that are not due to our intervention. The use of separate control sites (rather than randomizing some PCPs at each intervention site to control conditions) was preferred due to concerns about potential contamination across intervention and control conditions within sites. For both the control sites and the pre-intervention baseline period, we will identify patients who would have been eligible for the study; patients meeting criteria for multiple cohorts will be randomly allocated to only one.

Study Cohorts

The intervention cohort will consist of eligible patients in one of the three medication groups with an upcoming PCP appointment during the study enrollment period. We will create a comparison historical control cohorts comprising eligible patients in each medication group who were seen by the same PCPs at the same sites as our intervention cohort eighteen months to one year before our intervention cohort window to allow for comparable follow-up time before the intervention commenced. Patients in the intervention cohorts will be excluded from the historical control cohorts.

Medication Groups

To be enrolled in the study intervention or control cohort, patients needed to meet eligibility criteria for one of three medication-based groups. We have selected three medication-based patient groups based upon variations in 1) type of potentially inappropriate use, 2) medication factors (potential benefit and harms of continued use), and 3) anticipated interest in deprescribing by patients and providers.

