1. Proton Pump Inhibitor Cohort (PPI)

The PPI cohort will be defined as patients with prescriptions for any PPI at any dose for 90 consecutive days in patients of any age.

2. Diabetes – Hypoglycemia Risk (DM-HR)

To create diabetes cohorts, we identify overly-controlled patients with diabetes based upon International Classification of Diseases, Tenth Revision, Clinical Modification (ICD-10-CM) diagnosis codes, most recent HbA1c <7%, as well as one or more of the following criteria: 1) age 65 or older, 2) renal insufficiency defined as creatinine >2 mg/dL, or 3) cognitive impairment defined by a diagnosis of cognitive impairment and/or prescription for an acetylcholinesterase inhibitor (e.g., donepezil). Patients in the DM-HR group needed to have a current prescription for either insulin or sulfonylurea with at least 90 consecutive days on the medication in the prior year.

3. Gabapentin (Gaba)

The gabapentin cohort will include patients prescribed a total daily dose of gabapentin >1800mg for a minimum of 90 days.

Subject Exclusion Criteria

We will not exclude women or minorities, but children will not be eligible for participation.

1. Proton Pump Inhibitor Cohort (PPI)

In response to feedback from our pilot study, we will exclude diagnoses for which PPI continuation would be appropriate (e.g., Barrett’s esophagus, or those prescribed chronic glucocorticoids or NSAIDs).

2. Diabetes – Hypoglycemia Risk (DM-HR)

No exclusion criteria.

3. Gabapentin Cohort (Gaba)

We will exclude patients with recommended indications for gabapentin, including documented neuropathic pain using established criteria, those with seizure disorders, documented neuropathic pain, and cancer-related pain.

Recruitment

As we did for our IRB approved pilot study, we are requesting a waiver of informed consent and a waiver of HIPAA authorization to identify eligible Veterans to whom we will mail brochures.

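### Dropping historical controls who later enter an intervention cohort selects the control arm on an event linked to its own outcome; this probably understates the brochure effect, by an amount the documents do not allow us to size

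*Protocol*

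**What the plan says.** **The rule.** Protocol, Study Cohorts: "Patients in the intervention cohorts will be excluded from the historical control cohorts". Controls are eligible patients of the same PCPs at the same sites, seen "eighteen months to one year before our intervention cohort window", the stated purpose being "to allow for comparable follow-up time before the intervention commenced".

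**The windows.** Protocol, Randomization: PCPs are randomized to a drug group "at the beginning of the first (month 1) and second (month 7) window" and take their "remaining medication group at the start of the third (month 13) window".

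**Entry to an intervention cohort.** Protocol, Study sites: patients must be eligible and "are prescribed the target medication at the time of their scheduled primary care visit". Under Medication Groups, PPI entry needs "prescriptions for any PPI at any dose for 90 consecutive days". Gabapentin entry means being "prescribed a total daily dose of gabapentin >1800mg for a minimum of 90 days". The diabetes group needs a current insulin or sulfonylurea prescription with at least 90 consecutive days of use in the prior year.

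**The outcome.** Protocol, Study Measures: no refill in the 6 months after the visit, or a lower total daily dose (for insulin, cessation only).

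**The SAP.** It describes the two groups as matched on eligibility. It does not mention the exclusion, count the patients it removes, or plan a sensitivity analysis for it.

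**The concern.** Whether a control stays in the analysis depends on something that happens after the control's own visit. A control who stopped the drug and stayed off it cannot re-enter for that drug and is kept. A control who carried on can re-enter, and is then dropped. The brochure arm keeps its long-term users, while the control arm loses those of its long-term users who return.

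This acts directly on the control rate in the primary contrast, so the odds ratio is at stake. No planned step removes it. The covariates do not measure later re-entry. Provider nesting, removal of deaths and imputation address other problems. The control-site trend analysis, as described in the SAP, concerns sites with no intervention cohort, so the rule removes nobody there. The strength of the selection may also differ by drug, because the entry rules differ, so the test of moderation by medication is exposed too.

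**Working it through.** **1. Timing.** A control's index visit is the anchor month minus 18 to 12 months, and the outcome closes 6 months after the visit. The documents leave open whether the anchor is month 1 or each drug window.

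| Anchor | Control index visits | Outcome closes |
|---|---|---|
| Month 1 | −17 to −11 | −11 to −5 |
| Month 7 | −11 to −5 | −5 to 1 |
| Month 13 | −5 to 1 | 1 to 7 |

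With month 1 as anchor, every control outcome closes before any brochure enrollment begins. With window anchoring, same-drug re-entry with the same PCP still comes at least 6 months after the outcome closes (12 − 6). However, a month-13 control could receive a window-1 brochure for another drug during follow-up. Excluding that patient prevents contamination.

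**2. Link between outcome and re-entry.**
- Clear: cessation without restart; gabapentin reduced to 1800 mg/day or below.
- Weaker: non-refill where the order stays open or has merely expired; restarters.
- Weak: PPI dose reduction (any dose qualifies), sulfonylurea dose reduction, entry through another drug. PPI is 1,990 of 1,990 + 894 + 758 = 3,642 planned brochures, or 55%.

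**3. The SAP's own figure.** Inputs: 4.21% versus 6.55%, ICC 0.05, 20 patients per provider, 20% attrition, two-sided 0.05. The design effect is 1 + 19 × 0.05 = 1.95. Assuming equal arms with attrition in both, effective n per arm is 3,642 × 0.8 / 1.95 = 1,494. A two-proportion z test then has 81% power, against the stated 80%. The figure reproduces, so 4.21% versus 6.55% is a sound pair for illustration.

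**4. Effect of the rule.** Let p be the true control rate, f the re-entry share of non-deprescribed controls and g that of deprescribed controls.

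Retained control rate = p(1−g) / [p(1−g) + (1−p)(1−f)].

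Control odds are multiplied by (1−g)/(1−f), so the crude odds ratio is multiplied by (1−f)/(1−g). It is understated if g < f, unchanged if g = f and overstated if g > f.

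True odds ratios: (0.0655/0.9345)/(0.0421/0.9579) = 1.59. At the 15% brochure rate that the SAP calls reasonable, (0.15/0.85)/(0.0421/0.9579) = 4.02.

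| f | g (assumed) | Factor | Control rate | OR 1.59 reads | OR 4.02 reads |
|---|---|---|---|---|---|
| 10% | 7.5% (0.75f) | 0.973 | 4.32% | 1.55 | 3.91 |
| 30% | 22.5% (0.75f) | 0.903 | 4.64% | 1.44 | 3.63 |
| any | equal to f | 1 | 4.21% | 1.59 | 4.02 |
| 25% | 31.25% (1.25f) | 1.091 | 3.87% | 1.74 | 4.38 |

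All values of f and g are assumptions; the documents give no overlap count.

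**5. No power loss is quoted.** Starting power alone is 81% with attrition in both arms, 85% with attrition in the brochure arm only and 89% with none. The design effect also falls as controls per provider are removed. The documents settle neither choice.

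**The case against.** **The rule is an open design choice with a purpose.** It is stated plainly and keeps each patient in one arm of a model that nests patients only within providers. The claim of matched eligibility can fairly be read as drug-based eligibility at the visit, which this rule does not contradict. That stands. But independence can be secured with a patient-level error term, without conditioning on a later event.

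**Size and direction are not in the documents.** This also stands. Deprescribed patients can re-enter by the routes listed above, and if frequent attenders are both deprescribed more and seen again more, g could exceed f and the bias would reverse.

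**A reader might infer more.** One stronger reading is that no deprescribed control can return (g = 0). On that reading f = 37% would erase the planned difference, since 1 − 1/1.595 = 0.373. The documents do not support g = 0: restarters, PPI and sulfonylurea dose reductions and entry through another drug all leave a way back. A second is that the trial loses its power. That loss cannot be derived, and at a 15% brochure rate significance is not threatened over the range shown; only the effect size shifts.

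**The control sites could help.** Their planned trend analysis does not show the problem, but the protocol does identify would-be-eligible patients there. That is a resource for the fix.

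**Conclusion.** The point holds as a structural weakness of unknown size. The exclusion conditions the control arm on later drug use that is linked to its own outcome; the brochure arm has no counterpart, and nothing in the SAP corrects it. An odds ratio that is too small is probable, because lasting cessation and gabapentin reductions to the threshold or below block same-drug re-entry.

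That conclusion rests on g < f, which the entry rules make likely but do not guarantee. The table above shows sensitivity to assumed values and is not an estimate of bias. The matter should be fixed, with medium confidence: the mechanism is clear, the magnitude is open, and the check is cheap.

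**What to change.** - **Control definition.** Define historical controls only by information available at their own index visit, and keep those who later become eligible. As one stated exception, exclude or censor those whose 6-month follow-up overlaps a brochure mailing to them. That exception also uses a later event, so report its count separately.
- **Repeated patients.** Account for patients who appear in both periods with a patient-level cluster or robust error in addition to provider nesting.
- **Anchor.** State which window anchors the control period. Month-1 anchoring removes the overlap with mailings, but it is not free. With 6-month windows (an assumption), window-3 patients in months 13 to 19 would be compared with controls from months −17 to −11. That is a gap of 24 to 36 months, against 12 to 24 under window anchoring, and temporal trend is a threat the protocol itself names.
- **Reporting.** The SAP is written in the past tense and its Missing Data section reports results. Keep the existing primary analysis. Report the number excluded by drug group and by the control's 6-month outcome, which gives f and g. Present the restored-control analysis beside it as a labelled post hoc sensitivity analysis, and describe the rule in the SAP as well as the protocol.
- **Supporting check.** Apply the same exclusion to control-site patients eligible in both periods. This estimates f and g without brochure exposure, though those sites are non-equivalent.

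Cost: one further query of the pharmacy data warehouse (CDW), a few sentences of text, and some within-patient correlation to model.

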It is possible that Veterans could feel discomfort receiving information about their medications, expressing their beliefs and perspectives, or have concerns that their subsequent health care services will be affected. Bringing the issue of potential medication overuse to Veterans' attention may also lead them to worry that they are taking too many medicines or that the targeted medications (PPIs, diabetes medications, or gabapentin) may have caused them harm.

The intervention could lead to the actual discontinuation of unnecessary medications as intended; nonetheless, there is a slight possibility that the intervention could unintentionally lead to discontinuation of medications that are necessary or that the discontinuation of medications perceived as unnecessary could actually result in adverse drug withdrawal events. It is also possible that patients will stop a medication after receiving the brochure but without consulting their primary care provider.

The risks of deprescribing medications include, but are not limited to, adverse drug withdrawal reactions and return of a medical condition. Adverse drug withdrawal reactions are rare, especially in comparison to adverse drug events. It is more common for patients to experience a return of symptoms for which the medication was initially prescribed. Serious adverse events resulting from inappropriately discontinuing a medication include upper gastrointestinal bleeding for the PPI cohort, diabetic ketoacidosis or hyperosmolar hyperglycemic state for the DM cohort, and seizure for the gabapentin cohort.

Risk from breach of confidentiality – The risk to participants includes potential compromise of confidential information; however, the use of VA data in research analyses similar to those proposed is standard practice and there are no viable alternatives to obtain this quantity and quality of data. We will take all actions required to protect the security and integrity of confidential and personal health information.

Procedures to Minimize Risk

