Veterans receiving the intervention (brochure) and survey – Exclusion criteria have been carefully incorporated to help minimize Veteran risk prior to enrollment. Further, as noted, we are not randomizing patients to have medications withdrawn. The primary intervention is distribution of information directly to patients. It is important to note that the decision to deprescribe or not remains in the purview of the patient-provider dyad. We will provide a brief cover letter when sending the medication-specific brochure to patients, and the medication-specific brochure states multiple times to not decrease or discontinue a medication without first consulting with a clinician. We are also mailing the brochures two weeks prior to a primary care visit, so if patients decide they want to stop a medication, they will already have an appointment scheduled. Taken together with the fact that patients and providers already have the ability to make deprescribing decisions, the risk of this study is not greater than current standard practice.

Risk from breach of confidentiality – In order to assure appropriate research subject selection and high-quality data collection, all study personnel will undergo training in the study protocols. We will take all necessary steps to ensure the protection of confidential information in accordance with VA regulations and other applicable laws. All identifiable data will be protected from improper use or disclosure. Only research team members will have access to data. We will enter survey data into an electronic database with a unique identifier, removing any Protected Health Information (PHI). We will store all electronic data entirely within the VA network, which is protected by firewalls. User identification codes limit access to specific directories and files. We will not include names on audio-recordings or transcriptions, and publications will not identify individual participants or the sites from which they were recruited. We will not disclose identifiable information to any other person or entity outside VA, except as required by law, for authorized oversight of this research study, or for approved use in another study by an IRB. We will store physical data in locked cabinets within the Section of General Internal Medicine and Center for Healthcare Organization and Implementation Research (CHOIR) offices at VA Boston

Potential Benefits

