Per instructions of the VA HSR&D Program, the full Data Analysis Plan has been submitted to the Data Safety Monitoring Board (DSMB) using the Just-In-Time (JIT) document manager. Because the intervention described is an educational outreach to patients, there is minimal risk since clinical providers retain complete authority to deprescribe, de-escalate, and resume medications per their clinical judgement. However, it is possible that deprescribing could lead to adverse drug withdrawal. We expect these to be extremely rare occurrences, as we are identifying Veterans likely to be over-treated and further excluding populations for whom the medications are indicated. Thus, we will assess for serious adverse drug withdrawal events, specifically looking for emergency department and hospital visits for upper gastrointestinal bleeding for the PPI cohort, diabetic ketoacidosis or hyperosmolar hyperglycemic state for the DM cohort, and seizure for the gabapentin cohort on a quarterly basis for all recruited subjects.

Monitoring progress reports will be submitted to regulatory bodies (e.g., IRB) as requested and/or required. This will serve as a method for identifying systematic problems and allow the study team to identify and resolve problems and continuously maintain and improve data quality and Veteran safety. Additionally, we will schedule weekly team meetings to be led by the study PI and include all study personnel directly involved in enrollment, data collection, data entry and the intervention protocol. These team meetings will allow the study PIs to keep track of enrollment numbers, data integrity (e.g., reasons for missing data), and protocol implementation challenges that need to be addressed in a timely manner.

Adverse Event/Unanticipated Problems Reporting Plans

The Principal Investigator at VABHS will report Unanticipated Problems, Adverse Events, and safety monitors' reports to the IRB in accordance with VHA Handbook 1058.01 and VABHS IRB SOP. This is a multi-site study, but all procedures will be conducted at VABHS and thus oversight remains with the VABHS IRB.

References

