Official Title: Engaging Patients to Promote Deprescribing

NCT Number: NCT04294901

Document Date: November 14, 2019

Statistical Power

Based on fiscal year (FY) 2017 data, we estimated that we would mail brochures to at least 1,990 PPI patients, 894 Diabetes-Hypoglycemia patients, and 758 Gabapentin patients during the study. For apriori statistical power analyses, we made the following assumptions based on our pilot data: an overall baseline deprescribing rate of 4.21%, a conservatively high intraclass correlation coefficient (ICC) of 0.05 (for non-independence among patients of the same provider), an average of 20 eligible patients per PCC or WHC provider, and a 20% attrition rate (i.e., patients who receive the intervention brochure but do not attend their clinic visit). With these assumptions, we determined that we would have 80% power (for two-tailed tests at $\alpha=0.05$) to detect deprescribing rates following the intervention as small as 6.55% overall for these low-end estimates of our projected sample. Moreover, even at these low-end estimates of the projected sample size, we determined we would have 80% power to detect an overall deprescribing rate as low as 15% among the combined intervention cohorts even if the ICC was as high as 0.1, the baseline deprescribing rate was as high as 10%, and/or the attrition rate was as high as 40%. Notably, a deprescribing rate of 15% was reasonable to expect given that we found similar or higher rates in our pilot study.

We conducted analyses using SAS.³

Endpoints & Covariates

The primary hypothesis was deprescribing would be greater for Veterans receiving the intervention brochure than for those in the historical control group.

The primary outcome was binary: deprescribing versus not, assessed via pharmacy dispensing data from the VA Corporate Data Warehouse (CDW). More specifically, six months from the index date, an analyst queried the CDW to determine medication outcomes (e.g., complete deprescribing, dose reduction). We selected 6 months because prescriptions are often filled as a 90-day supply and using a shorter observation window might not fully identify that the prescription was not refilled. We removed patients who died within six months from their index data from intervention and historical controls at the analysis stage to avoid misattributing deprescribing to the intervention rather than death.

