To identify dose reductions, we calculated the total daily dose (TDD) of the target medication as [dose*(quantity/days supplied)].^{1,2} Substitutions within a medication drug class (e.g., pantoprazole to omeprazole) were standardized to one medication within each class. We only compared TDD at 6 months to that at the index visit for oral medications because insulin dose adjustments are not consistently documented within the electronic health record. Combination insulin products were separated into their long acting and short acting components and analyzed separately. We allowed a 10% buffer for days' supply of PPI, sulfonylurea, and gabapentin (e.g., 33 days for a 30-day supply) to account for missed doses and 100% buffer for insulin due to dispensing requirements (e.g., minimum vials dispensed regardless of dose).

Patient factors and provider characteristics (age, gender, profession) were included as covariates in the model. Based on our conceptual model and using data from CDW, patient factors included age, race, sex, and Elixhauser comorbidities in the year prior to the scheduled primary care visit.^{4,5}

Additionally, we planned to examine whether the effectiveness of the brochure intervention was associated with target medication.

Interim & Final Analysis

Our primary comparisons were between “brochure-intervention” patients and “historical control” patients (matched in terms of eligibility) from the same primary care provider. To investigate the impact of the intervention brochure on deprescribing, Hierarchical Generalized Linear Modeling (HGLM) was used to account for the nesting of patients within providers. This approach provided information not just about the average effectiveness of the intervention, but also about how much variation there is in the intervention impact across providers. In all models, Level 1 (patient-level) intercepts and slopes were treated as random effects, and parameters were estimated with robust standard errors. Using this approach of nesting patients within providers at intervention sites, for our primary analysis, we compared the likelihood of deprescribing among patients in the pre-intervention (“historical”) period to that for patients in the intervention periods who were mailed the brochure. We predicted that intervention patients would be significantly more likely to have deprescribing than patients in the pre-intervention period with the same eligibility criteria. We then examined whether the

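### As written, the diabetes cohort admits insulin users with type 1 diabetes who have HbA1c <7% and one added risk criterion, and nothing screens them out before the brochure is mailed

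*Protocol*

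**What the plan says.** **Eligibility.** Under Medication Groups, the protocol says "we identify overly-controlled patients with diabetes based upon International Classification of Diseases, Tenth Revision" and goes on to require all of the following:

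- a most recent HbA1c <7%;
- at least one of age 65 or older, creatinine >2 mg/dL, or cognitive impairment;
- a current insulin or sulfonylurea prescription, with at least 90 consecutive days of use in the prior year.

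No diabetes type is stated and no code list is printed in either document. Under Subject Exclusion Criteria, the PPI and gabapentin cohorts each exclude patients whose use is indicated. The DM-HR entry is "No exclusion criteria". Apart from that, only children are ineligible.

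**Outcome.** Study Measures counts only complete cessation for insulin; dose reduction counts for the oral drugs.

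**Risk.** The Risks section says "It is also possible that patients will stop a medication after receiving the brochure but without consulting their primary care provider". It names DKA and hyperosmolar hyperglycemic state (HHS) as the serious events for the diabetes cohort.

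**Safety rationale.** Procedures to Minimize Risk says "Exclusion criteria have been carefully incorporated to help minimize Veteran risk prior to enrollment". The Safety Monitoring Plan expects serious withdrawal events to be very rare, "as we are identifying Veterans likely to be over-treated and further excluding populations for whom the medications are indicated".

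**The concern.** HbA1c <7% together with age, renal function or cognition is a reasonable screen for over-control. It does not separate patients who might manage without insulin from patients who cannot. Singling out type 1 diabetes is a clinical judgement that the documents do not make. It does follow the protocol's own approach in the other two cohorts, which is to remove patients whose continued use is appropriate before contacting them.

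What is at stake is an avoidable risk of DKA in a small group, in a study that requests a waiver of informed consent. Bias in the treatment comparison is not the issue.

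**Working it through.** **1. Eligibility check.** Take a 66-year-old with a type 1 code, HbA1c 6.8% and continuous insulin.

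| Stated rule | Met? |
|---|---|
| Diabetes by ICD-10-CM code, type unspecified | Yes |
| HbA1c <7% | Yes |
| Age 65 or older, creatinine >2 mg/dL, or cognitive impairment | Yes (age) |
| Insulin or sulfonylurea, at least 90 consecutive days | Yes |
| Any DM-HR exclusion | None stated |

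A type 1 patient under 65 with normal creatinine and cognition is not eligible, so the gap is narrower than all type 1 insulin users with HbA1c <7%.

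**2. Does any other safeguard screen before mailing?** The brochure's advice to consult a clinician before any change, the clinician emails and the prescriber's retained authority all act once the patient has been selected. The DKA/HHS checks act after an event. The scheduled visit helps ("We are also mailing the brochures two weeks prior to a primary care visit"), but the SAP's power section assumes 20% attrition, defined as "patients who receive the intervention brochure but do not attend their clinic visit", and considers up to 40%. Applied to DM-HR, 894 × 0.20 = 178.8 and 894 × 0.40 = 357.6 recipients without the visit. These are whole-sample planning rates, and missing a visit does not mean stopping insulin.

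**3. The plan's power figure.** Inputs from the SAP's Statistical Power section: 1,990 + 894 + 758 = 3,642 mailings, 20% attrition, ICC 0.05, 20 patients per provider, 4.21% versus 6.55%, two-sided 0.05. An equal-sized historical group is assumed, because the SAP does not state its size.

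- Design effect: 1 + 19 × 0.05 = 1.95.
- Effective n per group: 3,642 × 0.8 / 1.95 = 1,494.2.
- Power = Φ{[Δ√n − 1.96√(2p̄q̄)] / √(p₁q₁ + p₂q₂)}, with Δ = 0.0234 and p̄ = 0.0538.
- Numerator: 0.0234 × 38.655 − 1.96 × 0.31908 = 0.2791. Denominator: 0.31865. Φ(0.876) = 0.8095.

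This agrees with the stated 80%.

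**4. Power after a type 1 exclusion.** The share removed is an assumption.

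| Share of DM-HR removed | Patients | Effective n per group | Power |
|---|---|---|---|
| 0% | 0 | 1,494.2 | 0.8095 |
| 5% | 45 | 3,597 × 0.8 / 1.95 = 1,475.7 | 0.8047 |
| 10% | 89 | 3,553 × 0.8 / 1.95 = 1,457.6 | 0.7998 |

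**5. Number affected.** At an assumed 1%, 3% or 5% of 894, this is 8.9, 26.8 or 44.7 patients mailed.

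**6. Effect on the primary estimate.** At the 5% share, 44.7 / 3,642 = 0.01227 of the sample. If this group's rate were 0% instead of 6.55%, the pooled rate would move by 0.01227 × (0 − 6.55) = −0.08 percentage points. If it were 15%, the shift would be 0.01227 × (15 − 6.55) = +0.10 points.

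**The case against.** **The code list may already restrict type.** This stands. An absence of exclusions does not prove inclusion, because the inclusion codes could be limited to type 2. The point therefore concerns the rule as stated. A reader might infer that type 1 patients were in fact mailed; the documents do not show that.

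**The safety statements are study-wide.** This also stands in large part. A reader might infer that the two statements on exclusions are false for the 894 of 3,642 projected recipients (24.5%) in DM-HR. Neither statement promises an exclusion in every cohort. The Safety Monitoring Plan gives two grounds, and DM-HR can rest on the first, likely over-treatment. The wording is loose rather than false.

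**The plan has considered harm in this cohort.** The Recruitment section's note on cognitive impairment argues that patients too impaired to use the brochure face more danger from hypoglycemia than from hyperglycemia, even if they stop unsupervised. That is a considered position, but it does not address type 1 diabetes.

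**Monitoring already exists.** Correct: DKA/HHS emergency and hospital visits are checked quarterly for all recruited subjects, and diagnoses are followed for a year after the index visit. The only missing element is a breakdown by diabetes type.

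**The numbers are assumed and small.** Also correct. The 1% to 5% share has no basis in the documents.

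**Conclusion.** The point holds for the eligibility rule as written: type 1 insulin users with HbA1c <7% and at least one added risk criterion qualify, and no listed safeguard removes them before mailing. It is worth fixing because the possible event is serious and the change is cheap, although the group is probably small.

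The conclusion rests on the printed text, on the clinical judgement that type 1 patients depend on insulin, and on an assumed type 1 share. Two stronger readings are not supported:

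- **Excess DKA.** The documents give neither a type 1 share nor an event rate, so no number of DKA cases can be derived.
- **Bias in the primary comparison.** Even at a 5% share, the shift is between −0.08 and +0.10 percentage points.

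**What to change.** **If mailing is not complete:**

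1. Exclude type 1 diabetes codes from DM-HR, identically in the brochure, historical and control-site cohorts, and print the ICD-10-CM list. If the list already omits type 1, printing it settles the eligibility question.
2. Reword the Safety Monitoring Plan so that exclusion of indicated use is tied to PPI and gabapentin, and DM-HR rests on over-control plus the type 1 exclusion.

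The cost is one code list in the existing data query, one sentence, and a slightly smaller DM-HR cohort with the small power loss shown above.

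**If mailing is complete**, as the SAP's past tense suggests, eligibility can no longer change. Flag type 1 patients from their codes and report the DKA/HHS events already being collected separately for them, including those who missed the visit. This costs one flag and one table. A sensitivity analysis without these patients is not needed, given the size of the shift.
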